1. MTX
2. Upadacitinib 15 mg QD
3. Upadacitinib 30 mg QD
4. MTX → Upadacitinib 15 mg QD + MTX
5. MTX → Upadacitinib 30 mg QD + MTX
6. Upadacitinib 15 mg QD → Upadacitinib 15 mg QD + MTX/csDMARD
7. Upadacitinib 30 mg QD → Upadacitinib 30 mg QD + MTX/csDMARD

For Japan sub-study, there are three additional exposure sequences:

8. Upadacitinib 7.5 mg QD
9. MTX → Upadacitinib 7.5 mg QD + MTX
10. Upadacitinib 7.5 mg QD → Upadacitinib 7.5 mg QD + MTX/csDMARD

Starting with Amendment 5.01.01 (for Japan) and Amendment 6 (for global), subjects receiving upadacitinib 30 mg QD will be switched to upadacitinib 15 mg QD. For these subjects, adverse events and exposure to upadacitinib 30 mg QD will be censored at the time of dose switch; subsequent adverse events and exposure starting the day of first dose

of upadacitinib 15 mg QD will be summarized under separate groups, as described in Section 8.1. Assessment of potentially clinically significant laboratory and vital sign values will be based on the same treatment exposure groups as for adverse events, as described above. For summary of mean change from baseline in laboratory values and vital signs, exposure sequences 3, 5 and 7 (i.e., subjects who switched from upadacitinib 30 mg QD to 15 mg QD) will be censored at the time of dose switch. Mean change from baseline for laboratory values and vital signs collected after dose switch will be summarized separately by visits post switch.

10.2 Analysis of Adverse Events

A treatment-emergent Adverse Event (TEAE) is defined as an adverse event with an onset date that is after the first dose of study drug, and no more than 30 days of the drug after the last dose of study drug.

Events where the onset date is the same as the study drug start date are assumed to be treatment-emergent, unless the study drug start time and the adverse event start time are collected and the adverse event start time is prior to the study drug start time. If an incomplete onset date was collected for an adverse event, the event will be assumed to be treatment-emergent unless there is other evidence that confirms that the event was not treatment-emergent (e.g., the event end date was prior to the study drug start date).

Adverse event data will be presented by SOCs and PTs using MedDRA version 19.0 or most up to date version. All adverse event tables will be sorted in alphabetical order by SOC and PT and descending percentages for each treatment group.

10.2.1 Analysis of Adverse Events Prior to Protocol-Defined Treatment Switching at Week 26

10.2.1.1 Adverse Events Overview

The number and percentage of subjects experiencing TEAEs will be summarized by "as treated" treatment group for the following AE categories.

- All TEAEs
- Treatment-emergent serious adverse events (SAEs)
- Treatment-emergent severe adverse events
- TEAEs reasonably possibly related to study drug
- TEAEs of special interest
- TEAEs leading to discontinuation of study drug
- TEAE leading to death

In the AE overview summary, any event with an unknown severity will be considered as severe and any AE with an unknown relationship will be considered as having "reasonable possibility" of being related to study drug.

Additional AEs may be considered for tabulation/summary based on recommendations from Clinical and Safety as deemed appropriate.

For TEAEs of special interest, the point estimate and 95% CI (using normal approximation) will be provided for the treatment difference in AE percentage between each Upadacitinib dose group and the MTX group.

As a sensitivity analysis, the AE overview summary will be repeated by randomized treatment groups. In this summary, all AEs with an onset date after the first dose of study drug will be included, regardless of whether the AE occurred more than 30 days after the last dose of study drug.

10.2.1.2 Adverse Events by System Organ Class and Preferred Term

The number and percentage of subjects experiencing adverse events will be tabulated by SOC and MedDRA PT by "as treated" treatment group. The SOCs will be presented in alphabetical order, and the PTs will be presented in alphabetical order within each SOC.

The following summaries of adverse events will be generated:

- All TEAEs

- Treatment-emergent serious adverse events (SAEs)
- Treatment-emergent severe adverse events
- TEAEs reasonably possibly related to study drug
- TEAEs leading to discontinuation of study drug
- TEAE leading to death
- Frequent AEs (reported in 2% of subjects or more in any treatment group)

Subjects reporting more than one adverse event for a given MedDRA preferred term will be counted only once for that term (most severe incident for the severity tables and most related incident for the relationship tables). Subjects reporting more than one type of adverse event within a SOC will be counted only once for that SOC. Subjects reporting more than one type of adverse event will be counted only once in the overall total.

As a sensitivity analysis, the AE summary by SOC and PT will be repeated by randomized treatment groups. In this summary, all AEs with an onset date after the first dose of study drug will be included, regardless of whether the AE occurred more than 30 days after the last dose of study drug.

10.2.1.3 TEAEs by Maximum Severity

TEAEs will also be summarized by maximum severity by "as treated" treatment group and overall. If a subject has an AE with an unknown severity, then the subject will be counted in the severity category of unknown, even if the subject has another occurrence of the same event with a severity present. The only exception is that if the subject has another occurrence of the same AE with the most extreme severity – severe. In this case, the subject will be counted under the severe category.

10.2.1.4 TEAEs by Maximum Relationship

TEAEs will also be summarized by maximum relationship to Upadacitinib and Placebo, as assessed by the investigator, by "as treated" treatment group and overall. If a subject has a TEAE with an unknown relationship, then the subject will be counted in the relationship category of "unknown," even if the subject has another occurrence of the

same event with a relationship present. The only exception is if the subject has another occurrence of the same TEAE with a relationship assessment of "reasonable possibility." In this case, the subject will be counted under the "reasonable possibility" category.

10.2.1.5 Frequent ($\geq 2\%$) Adverse Events and Reasonably Possibly Related Adverse Events by System Organ Class and Preferred Term

TEAEs and reasonably possibly related AEs occurring for more than 2% of the subjects in any of the "as treated" treatment groups will be summarized by MedDRA PT in decreasing frequency separately.

10.2.1.6 Adverse Events of Special Interest

The Adverse Events of Special Interest (AESI) categories will be summarized and presented by "as treated" treatment group and overall using SOC and MedDRA PT. The AESI categories will be identified per Standard MedDRA Queries (SMQs)/Company MedDRA Queries (CMQs) in [Table 12](#) below. Adjudicated cardiovascular events will be summarized and presented by treatment group using the CAC adjudicated categories.

Table 12. AESI for Upadacitinib with SMQs/CMQs/PTs Searches

AESI	Type of MedDRA Query	Broad or Narrow Search	SMQ/CMQ Search Criteria
Serious Infections	CMQ		"Infections" – Subset for SAEs
Opportunistic Infection excluding Tuberculosis and Herpes Zoster	CMQ		"Opportunistic Infection excluding Tuberculosis and Herpes Zoster"
Possible Malignancy	SMQ	Narrow	"Malignancies"
Malignancy	SMQ		"Malignant tumours"
Non-Melanoma Skin Cancer (NMSC)	SMQ	Narrow	Skin Malignant tumours (Narrow SMQ) removing Melanoma CMQ
Malignancy excluding NMSC			"Malignant tumours" SMQ removing NMSC output
Lymphoma	SMQ		"Malignant Lymphomas"
Hepatic Disorder	SMQ	Narrow	"Drug Related Hepatic Disorders"
Adjudicated Gastrointestinal Perforations	Output from adjudication		
Anemia	CMQ		"Non-Hemolytic and Non-Aplastic Anemias"
Neutropenia	CMQ		"Hematological Toxicity – Neutropenia"
Lymphopenia	CMQ		"Hematological Toxicity – Lymphopenia"
Herpes Zoster	CMQ		"Herpes Zoster"
Creatine Phosphokinase (CPK) Elevation	PT		Search only for the PT of "Blood creatine phosphokinase increased"
Renal Dysfunction	SMQ	Narrow	"Acute Renal, Failure"
Active Tuberculosis	CMQ		"Active Tuberculosis"
Adjudicated Cardiovascular Events	Output from CAC		
MACE*			
Cardiovascular Death			
Non-fatal Myocardial Infarction			
Non-fatal Stroke			

Table 12. AESI for Upadacitinib with SMQs/CMQs/PTs Searches (Continued)

AESI	Type of MedDRA Query	Broad or Narrow Search	SMQ/CMQ Search Criteria
Undetermined/Unknown Cause of Deaths			
Other Cardiovascular events			
Adjudicated Thrombotic Events	Output From CAC		
Venous Thromboembolic Events**			
Deep Vein Thrombosis			
Pulmonary Embolism			
Other Venous Thrombosis			
Arterial Thromboembolic Events (non-cardiac, non-neurologic)			

CAC = Cardiovascular Adjudication Committee; CMQ = company MedDRA query; PT = preferred term; SMQ = standard MedDRA query

* MACE; Major Adverse Cardiovascular Events, defined as cardiovascular death, non-fatal myocardial infarction and non-fatal stroke.

** Venous thromboembolic events (VTE) include deep vein thrombosis (DVT) and pulmonary embolism (PE) (fatal and non-fatal).

Additional AEs may be considered for tabulation/summary based on recommendations from Clinical and Safety as deemed appropriate.

10.2.2 Analysis of Long Term Adverse Event Rates

Long term adverse event rates will be analyzed using event rates adjusted by cumulative exposure and will be based on the actual treatment received at the time of AE occurrence. Starting with Amendment 5.01.01 (for Japan) and Amendment 6 (for global), subjects receiving upadacitinib 30 mg QD will be switched to upadacitinib 15 mg QD. For these subjects, adverse events and exposure to upadacitinib 30 mg QD will be censored at the time of dose switch; subsequent adverse events and exposure starting the day of first dose

of upadacitinib 15 mg QD will be summarized under separate groups. The detailed treatment exposure groups, including the handling of dose switch, are described in Section 8.1.

10.2.2.1 Overview of Adverse Events Rates per 100 Patient-Years of Study Drug Exposure

An overview of AEs per 100 patient-years of study exposure will be presented by treatment group and overall for the following AE categories.

- All TEAEs
- Treatment-emergent serious adverse events (SAEs)
- Treatment-emergent severe adverse events
- TEAEs reasonably possibly related to study drug
- TEAEs of special interest
- TEAEs leading to discontinuation of study drug
- TEAE leading to death

For this calculation, one year will be considered to be 365.25 days. For each treatment group, the numerator of the overall rate will be the total number of TEAEs reported for the event; that is, a subject can contribute more than one event to the numerator. For each treatment group, the denominator of the rates will be the total number of days exposed to study drug summed across all treated subjects divided by 365.25. The TEAE rate per 100 patient-years of exposure will be calculated as $(\text{[numerator/denominator]}) * 100$. The number of TEAEs reported (numerator), the total number of years of study drug exposure (denominator), and the TEAE rate per 100 patient-years will be presented for each treatment group and overall.

In the AE overview summary, any event with an unknown severity will be considered as severe and any AE with an unknown relationship will be considered as having "reasonable possibility" of being related to study drug. Additional TEAEs may be

considered for tabulation/summary based on recommendations from Clinical and Safety as deemed appropriate.

For TEAEs of special interest, the point estimate and 95% CI (using normal approximation) will be provided for the treatment difference in the TEAE rate per 100 patient years between each Upadacitinib dose group and the MTX group.

As a sensitivity analysis, the AE overview summary per 100 patient-years of study exposure will be repeated by exposure groups. In this summary, all AEs with an onset date after the first dose of study drug will be included, regardless of whether the AE occurred more than 30 days after the last dose of study drug. This sensitivity analysis will only be performed in final CSR.

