#### **8.1.5.2.1 Treatment-Emergent Adverse Events (TEAE)**

AEs will be coded using MedDRA. A TEAE is defined as AE that began or worsened in severity after initiation of study drug.

AEs starting more than 30 days following the last dose of study drug will not be included in summaries of TEAEs. For subjects who continued into Period 2, AEs that are reported in Period 2 will be summarized in the combined safety analysis of Period 1 and Period 2.

As a general safety summary, the number and percentage of subjects experiencing TEAEs will be summarized for each treatment group for the following AE categories:

- All AEs;
- All severe AEs;
- All reasonably possibly related AEs;
- All SAEs;
- Frequent AEs (reported in 2% of subjects or more in any treatment group);
- Frequent reasonably possibly related AEs (reported in 5% of subjects or more in any treatment group);
- Discontinuations due to AEs;
- Death.

Additional AEs may be considered for tabulation/summary based on recommendations from Clinical and Safety as deemed appropriate.

TEAEs will be summarized and presented by system organ classes (SOCs) and preferred terms (PTs) using MedDRA. The SOC's will be presented in alphabetical order, and the PTs will be presented in alphabetical order within each SOC.

TEAE will also be summarized by maximum severity and by maximum relationship.

The AEs of special interest (including but not limited to serious infection, opportunistic infection, herpes zoster, TB, gastrointestinal perforations, malignancies, MACE, renal dysfunction, anemia, increased CPK, drug-related hepatic disorders, and embolic and thrombotic events (non-cardiac, non-CNS)) will be summarized. Event rate (per 100 patient years) for AEs of special interest will also be summarized for the combined safety analysis of Period 1 and Period 2.

All AEs leading to discontinuation of study drug will be presented in listing format. A listing by treatment group of TEAEs grouped by SOC and MedDRA preferred term with subject identification numbers will be generated.

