10.2.2.2 Overview of Adverse Events Rates per 100 Patient-Years of Study Drug Exposure

For each treatment group, the TEAE rate per 100 patient-years of exposure will be calculated overall, for each SOC and each PT, for each of the following events:

- All TEAEs
- Treatment-emergent serious adverse events (SAEs)
- Treatment-emergent severe adverse events
- TEAEs reasonably possibly related to study drug
- TEAEs leading to discontinuation of study drug
- TEAE leading to death

For this calculation, one year will be considered to be 365.25 days. For each treatment group, the numerator of the overall rate, the SOC rate, or the PT rate, will be the total number of TEAEs reported overall, for the SOC, or for the PT, respectively; that is a subject can be counted more than once overall, for a SOC, and for a PT. For each treatment group, the denominator of the rates will be the total number of days exposed to study drug summed across all treated subjects divided by 365.25. The TEAE rate per 100 patient-years of exposure will be calculated as $[(\text{numerator}/\text{denominator})]*100$. The

number of TEAEs reported (numerator), the total number of years of study drug exposure (denominator), and the TEAE rate per 100 patient-years will be presented overall, for each SOC, and for each PT for each treatment group.

As a sensitivity analysis, the AE summary per 100 patient-years of study exposure by SOC and PT will be repeated by exposure groups. In this summary, all AEs with an onset date after the first dose of study drug will be included, regardless of whether the AE occurred more than 30 days after the last dose of study drug. This sensitivity analysis will only be performed in final CSR.

10.2.2.3 Adverse Events of Special Interest Rates per 100 Patient-Years of Study Drug Exposure

The Adverse Events of Special Interest (AESI) categories will be summarized and presented for each treatment group and overall using SOC and MedDRA PT (for adjudicated cardiovascular events, the CAC adjudicated categories will be used). The AESI categories will be identified per Standard MedDRA Queries (SMQs)/Company MedDRA Queries (CMQs).

For each treatment group, the treatment-emergent Adverse Events of Special Interest (AESI) rate per 100 patient-years of exposure will be calculated overall, for each SOC and each PT, for each of the AESI listed in Section [10.2.1.6](#).

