For this calculation, one year will be considered to be 365.25 days. For each treatment group, the numerator of the overall rate, the SOC rate, or the PT rate, will be the total number of TEAEs reported overall, for the SOC, or for the PT, respectively; that is a subject can be counted more than once overall, for a SOC, and for a PT.

For each treatment group, the denominator of the rates will be the total number of days exposed to study drug summed across all treated subjects divided by 365.25. Please refer to Section [8.1](#) for the calculation of study drug exposure. The TEAE rate per 100 patient-years of exposure will be calculated as $[(\text{numerator}/\text{denominator})]*100$. The number of TEAEs reported (numerator), the total number of years of study drug exposure

(denominator), and the TEAE rate per 100 patient-years will be presented overall, for each SOC, and for each PT for each treatment group.

10.2.2.4 Listing of Serious Adverse Events (Including Deaths) and Adverse Events Leading to Study Drug Discontinuation

All serious adverse events (SAEs), deaths, and adverse events leading to discontinuation of study drug will be listed.

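### The long-term AESI rate difference versus MTX gets a normal-approximation 95% CI on event totals, with no small-count rule and no allowance for repeat events in one subject

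*SAP*

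**What the plan says.** SAP Section 10.2.2.1 defines the long-term rate as the total number of treatment-emergent events divided by total patient-years. On the numerator it adds: "that is, a subject can contribute more than one event to the numerator". For adverse events of special interest it then states that "the point estimate and 95% CI (using normal approximation) will be provided for the treatment difference in the TEAE rate per 100 patient years", comparing each upadacitinib dose group with MTX. It names no variance.

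The sentence belongs to an overview table: "An overview of AEs per 100 patient-years of study exposure will be presented by treatment group and overall for the following AE categories". AESIs are one of the seven categories listed. Rates for the individual AESIs come in Section 10.2.2.3, where the "rate per 100 patient-years of exposure will be calculated overall, for each SOC and each PT, for each of the AESI listed" in Section 10.2.1.6. That section promises counts, patient-years and rates, "and the TEAE rate per 100 patient-years will be presented overall, for each SOC, and for each PT for each treatment group", and mentions no difference or interval.

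The AESI categories are in Table 12 ("AESI for Upadacitinib with SMQs/CMQs/PTs Searches"). Several are nested: malignancy, non-melanoma skin cancer and malignancy excluding non-melanoma skin cancer; MACE and its components; venous thromboembolism and its components. On the exposure groups, Section 10.2.2 says: "The detailed treatment exposure groups, including the handling of dose switch, are described in Section 8.1".

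The protocol (Section 8.1.5.2.1) asks for less: "Event rate (per 100 patient years) for AEs of special interest will also be summarized for the combined safety analysis". The interval is therefore an SAP addition.

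**The concern.** A normal-approximation interval for a difference of two rates needs enough events in each group and a variance that reflects how the events arise. The plan secures neither.

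- **Sparse rows.** Table 12 includes lymphoma, active tuberculosis, gastrointestinal perforation and pulmonary embolism. Under the plug-in variance a group with no events adds nothing to the standard error, so the interval is short exactly when information is least.
- **Repeat events.** The numerator counts every event. If some subjects are more prone to events than others, the total varies more than a Poisson count and a Poisson variance is too small.

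This is the plan's only comparative interval for long-term AESIs against MTX, and SAP Section 11.1 says that the current version governs that reporting. What is at stake is an interval read at face value: too reassuring about a rare event with a true excess, or too precise for a row with recurrent events.

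**Working it through.** The plan gives no figure for these intervals, so there is nothing to reproduce. The check is of the method's coverage.

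**Inputs from the documents.** 300 subjects are planned per global arm and treatment lasts up to 260 weeks. The ceiling per arm is 300 × 260 × 7 / 365.25 = 1,495 patient-years (PY), before dropout and before MTX exposure is censored at rescue.

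**Assumed inputs.** Exposure of 900 or 1,000 PY for upadacitinib and 700 or 750 PY for MTX (47-67% of the ceiling); event rates as shown; and, for repeat events, a gamma frailty with variance k.

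**1. Sparse rows.** The plug-in interval is e1/T1 − e0/T0 ± 1.96 × √(e1/T1² + e0/T0²), where e is the event count and T the patient-years.

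*No events in either group, 900 and 750 PY.* The standard error is √(0 + 0) = 0 and the interval is [0, 0]. The score limits are −1.96²/750 and +1.96²/900, that is −0.51 to 0.43 per 100 PY.

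*A true excess over an MTX rate of 0.1 per 100 PY.* MTX then expects 0.70 or 0.75 events and has none with probability e^(−0.70) = 0.50 or e^(−0.75) = 0.47. Exact enumeration of two Poisson counts gives this plug-in coverage (%):

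| Upadacitinib rate per 100 PY | 900/700 PY | 900/750 PY | 1000/700 PY | 1000/750 PY |
|---|---|---|---|---|
| 0.3 | 92.1 | 92.2 | 93.9 | 93.8 |
| 0.4 | 95.0 | 94.8 | 89.6 | 89.7 |
| 0.5 | 92.6 | 92.5 | 93.9 | 93.7 |

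Across the 12 settings the interval lies wholly below the true excess in 4.4-9.3% of trials and wholly above it in 0.6-1.1%. The score interval covers in 96.5-98.4%. Counts are discrete, so coverage moves irregularly: with 1,000 PY in each group it is 86% at 0.2 v 0.1 and 93% at 0.3 v 0.1.

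*Where the problem stops.* At 900/750 PY, plug-in coverage is 94.6% at 0.3 v 0.3, 95.2% at 0.5 v 0.3 and 95.3% at 1 v 1. With equal rates of 0.1 or 0.2 it is 95.6-99.1% over the four exposure pairs.

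**2. Repeat events.** With mean m events per subject and frailty variance k, the count's variance-to-mean ratio is 1 + k·m. Take 300 v 250 subjects followed for 3 years each (900/750 PY).

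Worked case, 25 v 20 per 100 PY and k = 2:

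- m = 0.75 and 0.60, so the ratios are 1 + 2 × 0.75 = 2.5 and 1 + 2 × 0.60 = 2.2.
- Poisson variance: 300 × 0.75/900² + 250 × 0.60/750² = 0.0002778 + 0.0002667 = 0.0005444.
- Actual variance: 0.0002778 × 2.5 + 0.0002667 × 2.2 = 0.001281.
- Standard-error ratio: √(0.001281/0.0005444) = 1.53.
- Coverage: 2Φ(1.96/1.53) − 1 = 0.80.

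Simulation (20,000 runs), coverage in % with the Poisson variance:

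| Rates per 100 PY | k = 0.5 | k = 1 | k = 2 |
|---|---|---|---|
| 6 v 4 | 93.9 | 93.1 | 91.4 |
| 10 v 8 | 93.7 | 91.9 | 88.9 |
| 25 v 20 | 90.5 | 86.6 | 79.8 |

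A variance computed between subjects gives 94.8-95.2% in all nine settings. With no clustering, the Poisson variance gives 94.9-95.1% at these rates, so the loss comes from repeat events and not from the normal approximation.

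**The case against.** The strongest reply is that the SAP prescribes no variance formula. A score interval, or a subject-level variance with 1.96 limits, is also a normal approximation in a broad sense. That stands: the results above hold for the plug-in Poisson variance, which is the usual choice but is not stated. What remains is that the section states a method with no small-count or within-subject provision, and an analyst who follows it in the usual way gets these intervals.

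A second reply is that the wording points to a single overview row, so sparse categories may get no interval at all. This is fair, and which rows carry an interval is only missing detail. But the SAP defines no pooled AESI set, and a pooled row is where repeat events matter most.

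A third is that sparsity does harm only in a narrow region. This also stands: coverage is back to about 94-95% once the MTX rate reaches about 0.3 per 100 PY.

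Two stronger readings are tempting but not supported.

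- A reader might infer that the interval raises false alarms when a few events fall on upadacitinib and none on MTX. At 900/750 PY with equal rates of 0.1 and 0.2 per 100 PY, it excludes zero in only 0.9% and 3.7% of trials, below the nominal 5%.
- A reader might infer a biased comparison from SAP Section 8.1, which censors upadacitinib monotherapy at csDMARD addition but MTX only at rescue to upadacitinib plus MTX. Section 10.2.2.1 speaks of dose groups and does not commit to a monotherapy contrast.

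**Conclusion.** The point holds as a minor one. Under the plug-in Poisson variance, sparse rows can have zero-width intervals. With fewer than about one expected MTX event and a true excess, coverage is about 90-95% in the settings tabulated, and most misses understate the excess. Rows with repeat events are too narrow, with coverage of about 80-94% for frailty variance 0.5-2 and 6-25 events per 100 PY.

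The rates, exposure and frailty are assumed. The documents support no dispersion value, so coverage far below this range should not be claimed.

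Nor should a reader infer that a safety conclusion of the trial is at risk. The intervals are descriptive and carry no decision rule, counts and patient-years are printed beside each rate, serious events are listed, and the completed primary analysis is untouched.

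**What to change.** For the long-term analysis only, replace the normal-approximation wording in SAP Section 10.2.2.1 with two rules that never apply to the same row:

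1. If both groups have at least a pre-set number of events (for example 5), keep the event-rate difference and use a subject-level variance, robust or by subject bootstrap. Subjects rescued from MTX count in both the MTX group and an Any Upadacitinib group, so cluster by subject across groups.
2. Below that number, give a score (Miettinen-Nurminen) or exact-type interval for the difference in first-event incidence: subjects with an event over patient-years to first event. A subject-level variance does not help here, because it is also zero when there are no events. Label these rows, since the quantity differs from the event rate.

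The threshold of 5 is a suggestion. With about 5 or more expected events in each group and no clustering, plug-in coverage was 94.8-95.7%, so sparsity is no longer the issue there.

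State which rows carry an interval. If a pooled AESI row is shown, count each event once, because the Table 12 categories are nested.

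The cost is a few lines of SAP text and standard procedures on data already collected. The downside is somewhat wider intervals.
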